3.1.3 Allocation to Treatment Groups and Blinding

This is an unblinded, open-label study. A historical cohort will be used for comparison of the natural history of the AGS Scale.

3.2 Study Duration, Enrollment and Number of Sites

3.2.1 Duration of Study Participation

The study duration per subject will be up to 288 weeks, preceded by a screening period during which baseline testing will be obtained.

Study duration will be extended beyond Week 288 to long term follow up if transition to commercial supply is not possible for the patient.

3.2.2 Total Number of Study Sites/Total Number of Subjects Projected

The study will be conducted at one investigative site in the United States. It is expected that up to approximately 55 subjects may be enrolled, including those patients transferred from the JAGA Compassionate Use study (CHOP IRB Study #13205).

3.3 Study Population

Patients who meet all of the inclusion criteria (Section 3.4.1) and do not meet any of the exclusion criteria (Section 3.4.2) may enter the study (that is, sign consent). In addition, patients must meet the enrollment criteria in order to be eligible to receive baricitinib. The enrollment number of up to approximately 55 is an estimate based on the number of subjects required to obtain statistically significant results for efficacy, and accounting for those subjects who are found to be ineligible at screening, subjects withdrawn from participation for various reasons and replaced. The analysis of data obtained from these initially ineligible, but prospectively approved group of subjects entered to the study, will be assessed independently of the main group of subjects who meet all eligibility criteria. The impact of this group of subjects on the statistical analysis of this clinical protocol has been added to Section 6.4, "Sample Size and Power".

3.3.1 Patients from the Compassionate Use Treatment Protocol 14V-MC-JAGA

Patients previously enrolled in the Compassionate Use Treatment Protocol I4V-MC-JAGA (JAGA Compassionate Use study, CHOP IRB Study #13205) will automatically roll into this study and do not need to meet the eligibility criteria outlined below.

3.3.2 Inclusion Criteria

Identification of individuals appropriate for the study

Eligible patients will meet the following criteria:

- Clinical or molecular identification of Aicardi Goutières Syndrome including the following features
 - CSF or blood markers suggesting elevations of markers of interferon activation including CSF pleocytosis, elevation of interferon, and/or neopterin and tetrahydrobiopterin elevations
 - Evidence of neurologic disease on neuroimaging including intracranial calcifications and or a leukoencephalopathy
 - Clinical features of disease including features such as microcephaly, subacute encephalopathy, myopathy, spastic diplegia, skin involvement, autoimmune hepatitis, hematologic abnormalities
 - OR have documented mutations felt to be pathogenic in an AGS associated gene.
- Are ≥1 month of age.
- Are \geq 4.5 kg in body weight.
- Females after menarche must have a negative urine/serum pregnancy test and must use an acceptable method of contraception, including abstinence, a barrier method (diaphragm or condom), Depo-Provera, or an oral contraceptive, for the duration of the study.
- o Parental/guardian permission (informed consent).

3.3.2.1 Inclusion of Minorities and Children

The disorders to be investigated affect both genders and all different ethnic groups and we therefore expect to have proportional representation among the participants of the trials. These are rare disorders, and we will attempt to recruit all presenting potentially eligible patients. Most persons affected with AGS are children and thus pediatric patients will be included.

3.3.3 Exclusion Criteria

Patients will be excluded from the study if they meet any of the following criteria:

- Are pregnant or nursing at the time of entry or unable to use contraception as detailed below
 - Are females of childbearing potential (women >12 or who have had at least one menstrual period regardless of age) who are sexually active and who do not agree to use 2 forms of highly effective methods of birth control (see below) or remain abstinent during the study and for at least 28 days following the last dose of investigational product
 - Are sexually active males who do not agree to use 2 forms of highly effective birth control (see below) with female partners of childbearing potential or remain abstinent during the study and for at least 28 days following the last dose of investigational product.
 - Each of the following is considered a single highly effective method of birth control (the patient should choose 2):
 - oral, injectable, or implanted hormonal contraceptives
 - condom with spermicidal foam/gel/film/cream/suppository

- occlusive cap (diaphragm or cervical/vault caps) with spermicidal foam/gel/film/cream/suppository
- intrauterine device
- intrauterine system (for example, progestin releasing coil)
- vasectomized male (with the appropriate post-vasectomy documentation of the absence of sperm in the ejaculate)
- Overall health status that in the opinion of the investigator limits the safety of the use of baricitinib.
- Have been exposed to a live vaccine within 12 weeks prior to entry or are expected to need/receive a live vaccine (including herpes zoster vaccination) during the course of the study, with the exception of oral rotavirus vaccinations for which the time period is 2 weeks. Young patients who are not yet vaccinated and will be unable to receive live vaccines while they are receiving the program drug (baricitinib) may be included after a documented conversation by a physician not affiliated with the study or the Medical Monitor with the parents to ensure parental consent and understanding of the risk/benefit ratio of not receiving scheduled vaccinations. These subjects will only be included in the study after a physician obtaining consent also describes the risk/benefit ratio of not receiving scheduled vaccinations.
- Have the following evidence of renal insufficiency:
 - An estimated glomerular filtration rate (eGFR) based on the most recent available serum creatinine of <40 mL/min/1.73 m² if greater than 2 year of age. eGFR will be calculated using the *Bedside Schwartz Equation:* eGFR (mL/min/1.73 m²) = (0.413 x height) / S_{Cr}, with height measured in cm, and serum creatinine (S_{Cr}) in units of mg/dL.
 - Children with an eGFR of <40 mL/min/1.73 m² will not be enrolled, unless <24 months of age in which case a cut off of <30 ml/min/1.73 m2 will be used due to age-based differences in normal eGFR. Normal eGFR of <60 ml/min/1.73 m² is common in children <12 months, and a normal eFGR <40 ml/min/1.73 m² is common in infants <3-6 months.
 - The creatinine should be measured using the IDMS (Isotopic Dilution Mass Spectrometry) technique to monitor the eGFR if available. Other methods are allowed but are not preferred. Laboratory testing using other methods will not be used to monitor the eGFR.
- Have any of the following specific Hematologic abnormalities on screening laboratory tests (Appendices 10, 11, 12):
 - Hemoglobin <7 mg/dL (70 g/L). In infants <2 mo of age, 8 mg/dL will be used as a threshold
 - Neutropenia (absolute neutrophil count [ANC] <500 cells/µL)
 - CD4 <250 cell/µl on lymphocyte subset testing (where Absolute CD4 count=Absolute CD3/CD4 count=CD3/CD4 count=CD4 count=Absolute CD3+CD4+ cells)
 - Thrombocytopenia (platelets <30,000/µL). Patients who are on

anticoagulation or having a history of life-threatening bleeding should be excluded if platelet count is <50,000/µL

- Have any of the following infectious risks:
 - Evidence of active infection, at the time of entry or during the screening period, that in the opinion of the investigator, would pose an unacceptable risk for participating in the study
 - Ongoing or incompletely treated severe or systemic infection, excluding cellulitis/osteomyelitis that is felt to be attributable to AGS
 - Have had symptomatic herpes zoster infection within 12 weeks prior to entry or during the screening period
 - Have a history of disseminated/complicated herpes zoster (for example, multidermatomal involvement, central nervous system involvement or systemic involvement including hepatitis or pneumonitis)
 - Have a history of active hepatitis B, hepatitis C, or human immunodeficiency virus (HIV)
 - Have had household contact with a person with active tuberculosis (TB) and did not receive appropriate and documented prophylaxis for TB
- Have or have had a history of lymphoproliferative disease; or signs or symptoms suggestive of possible lymphoproliferative disease, or active primary or recurrent malignant disease; or been in remission from clinically significant malignancy for <5 years.
- Have liver abnormalities consistent with severe, chronic liver disease (Appendix 9).
- Have ECG or echocardiogram results that include an arrhythmia unamenable to standard treatment, severe pulmonary hypertension, severe heart valvular (greater than mild insufficiency or stenosis), or significant left heart failure (per AHA guidelines, an LVEF <50% is considered impaired) or right heart failure (RV function described as qualitatively more than mildly diminished systolic function), that in the consideration of the investigator places them at greater risk for participation in the study; have screening electrocardiogram (ECG) abnormalities that, in the opinion of the investigator, are clinically significant and indicate an unacceptable risk for the patient's participation in the study (for example, Bazett's corrected QT interval >450 msec for males and >470 msec for females); have echocardiogram results that, in the opinion of the investigator, places them at greater risk if included in the study.
- Are unable or unwilling to make themselves available for the duration of the study and/or are unwilling to follow study restrictions/procedures.
- Have received an immunosuppressive biologic agent/monoclonal antibody within 4 half-lives prior to entry, for example, anakinra (4 half-lives=18 hours); etanercept (4 half-lives=18 days); infliximab; or adalimumab (4 half-lives=36 days). Use is not indicated in subjects receiving Natalizumab, Nivolumab, Trastuzumab, Denosumab, and Belimumab. Use of IVIg is permitted.
- Have received or be currently treated with BCG (Intravesical), Cladribine, Dipyrone, Pimecrolimus, and Tacrolimus (Topical).

- Are currently enrolled in, or discontinued within the last 30 days from, a clinical trial involving an investigational product or non-approved use of a drug or device (other than the investigational product used in this study), or concurrently enrolled in any other type of medical research judged not to be scientifically or medically compatible with this study.
- Have screening laboratory test values outside the reference range for the population or investigative site that, in the opinion of the investigator, pose an unacceptable risk for the patient's participation in the study and are not attributable to AGS.
- Have screening thyroid-stimulating hormone and/or thyroxine values outside of the laboratory's reference range and are assessed to be clinically significant. If results are available from testing within 1 month, then the patient will not have to be retested. Patients who are receiving thyroxine as replacement therapy may participate in the study provided stable therapy has been administered.
- Have evidence of active or latent TB as documented by a positive purified protein derivative (PPD) test (≥5 mm induration between approximately 2 and 3 days after application, regardless of vaccination history), medical history, and chest x-ray at screening. The patient may also have a QuantiFERON®-TB Gold test. If the test is positive or indeterminate, the patient may undergo evaluation including a CXR and PPD and assessed for likely risk of active tuberculosis infection. In infants < 12 months of age, maternal and paternal testing can be used instead of testing the patient. Risk for TB will also be assessed using validated questions from The Red Book: Report of the Committee on Infectious Diseases (see below).

Validated Questions for Determining Risk of LTBI in Children in the United States

- Has a family member or contact had tuberculosis disease?
- Has a family member had a positive tuberculin skin test result?
- Was your child born in a high-risk country (countries other than the United States, Canada, Australia, New Zealand, or Western and North European countries)?
- Has your child traveled to a high-risk country? How much contact did your child have with the resident population?
- Have a positive test for hepatitis B defined as (1) positive for hepatitis B surface antigen, or (2) positive for anti-hepatitis B core antibody, but negative for hepatitis B surface antibody (unless the anti-hepatitis B core antibody is thought to be a false positive result). In the latter case, confirmation of the presence of hepatitis B virus (HBV) by DNA testing is required. An HBV DNA indeterminate result is considered HBV infection. If results are available from testing within the previous 3 months, then the patient will not have to be retested: If any of the hepatitis B tests have an indeterminate result, confirmatory testing will be performed by an alternate method. In infants < 3 months of age, maternal testing can be used instead of testing the patient.

- Have hepatitis C virus (positive for anti-hepatitis C antibody with confirmed presence of hepatitis C virus).
- Have evidence of HIV infection and/or positive HIV antibodies. If results are available from testing within the previous 3 months, then the patient will not have to be retested. In infants < 12 months of age, maternal testing can be used instead of testing the patient.
- Have HIV virus. In infants <12 months of age, maternal testing can be used instead of testing the patient.
- Taking a concomitant medication on the list of exclusion criteria (Appendix 16).

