4.4 Study Treatment Phase

4.4.1 Enrollment

Consent

Written informed consent from the patient/patient's parent or a legal guardian will be obtained in person by the study investigators prior to any study procedure, with the exception of blood and urine tests, and daily diaries, which may be completed from the pre-screening period, after verbal consent.

For the patients transferred from the JAGA Compassionate Use study (CHOP IRB Study #13205), written informed consent from the patient/patient's parent or a legal guardian will be obtained by the study investigators prior to any study procedure completed as part of this investigator-initiated study.

Additionally, all the JAGA subjects (including the patients who do not consent and transition to the investigator-initiated JAK inhibitor treatment in AGS study will be asked to sign a consent form to allow for their data collected as part of the compassionate use program to be used for data analysis as part of the investigator-initiated study. The JAGA subjects who do not transition to the investigator-initated study will sign a separate consent form while the subjects who transition will be re-consented with a revised informed consent form including mention of this data transfer. Statistical considerations of this data transfer are detailed in Section 6.

Inclusion criteria

Entered patients are eligible for enrollment into the study (that is, eligible to receive baricitinib) only if they meet inclusion criteria (Section 3.4.1) at the time of Visit 2 and don't meet the exclusion criteria listed in Section 3.4.2.

Exclusion from Study Enrollment

Entered patients are ineligible for enrollment (that is, ineligible to receive baricitinib) and should be discontinued from the study if they meet any of the exclusion criteria listed in Section 3.4.2.

Patients who are entered, but do not meet enrollment criteria, should be discontinued from the study. These patients can be re-entered into the trial (that is, be reconsented) if the investigator believes that the patient might meet enrollment criteria at a future date, taking into consideration the volume of blood required for rescreening. Patients will receive treatment as clinically indicated for infections regardless of treatment decisions for baricitinib.

Rationale for Exclusion of Certain Study Candidates

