4.4.2 Initial Treatment and Dose Escalation

Baricitinib will be dosed by patient age, weight range and eGFR. See Appendix 3 for the dosing schedule for patients with eGFR \geq 60 mL/min/1.73 m² or normal eGFR for patients age <24 months (eGFR \geq 60 mL/min/1.73 m²). eGFR will be calculated using the *Bedside Schwartz Equation:* eGFR (mL/min/1.73 m²) = (0.413 x height) / S_{Cr}, with height measured in cm, and serum creatinine (S_{Cr}) in units of mg/dL. The creatinine should be measured using the IDMS (Isotopic Dilution Mass Spectrometry) technique to monitor the eGFR if available. Other methods are allowed but are not preferred. Laboratory testing using other methods will not be used to monitor the eGFR. Tolerance will be judged by stability or improvement in hematology and chemistry laboratory test results collected as specified in Study Schedule (Appendices 1 and 2). See Appendix 4 for the dosing schedule for patients with eGFR 30 - <60 mL/min/1.73 m²).

Patients must receive a dose for at least 72 hours before a dose escalation can occur. Safety laboratory data will be assessed according to the Study Schedule (Appendices 1 and 2).

Every effort should be made to follow the dose escalation schedule shown in Appendices 3 and 4. However, if a patient's condition warrants an accelerated dose escalation schedule, dose reduction, interruption, or discontinuation, this may be allowed after review of the patient's clinical data and consultation with the subinvestigators. Additionally, in the event of AEs possibly attributable to the study drug, the dose may need to be reduced. These decisions should be taken following documented consultation, and agreement between the investigator and subinvestigators, and approval from the IRB prior to initiating the dose modification. Only in emergency situations will the investigator take subsequent dose restarts or increments after review of clinical data, documented agreement between the investigator and subinvestigators, and notification of the IRB.

Attention will be given to concomitant medications, in particular those that are exclusion criteria (Appendix 16).

Where needed, clinical pharmacists will be contacted about the need for dose adjustment and for guidance related to concomitant therapies that must be used with caution.

In the event that it is necessary to contact a clinical pharmacist, the study team can page the 24/7 on-call clinical pharmacist.

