Pharmacokinetic Sampling: Blood samples will be collected to determine baricitinib concentrations. Samples will be collected after beginning baricitinib therapy and at each dose increase at the time points shown in the Study timeline and may be collected at each study visit for safety monitoring. In these cases, PK sampling will occur at least 72 hours after dosing changes or at the next visit. PK testing may include a single measurement at 1.5 hours, or a full PK series at baseline, 1.5 hours and 4 hours post dose, and may include several doses during the day (eg morning and afternoon dose). For PK series, an IV will be placed. For single PKs, these will be drawn with the safety laboratory monitoring. PK samples may be banked for later analysis. As PK data become available, dosing adjustments may be required. Finally, changes in a subject's weight or renal function may require dose changes as the individual falls within different categories in the tables in Appendices 3 and 4. For example, this may occur in a child under 1 year of age with rapid weight gain.

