BID = twice daily, eGFR = estimated glomerular filtration rate, QID = 4 times daily, TID = 3 times daily.

a If there was a change in the patient's weight during the study, this would place the patient in a different weight range.

b Based on adult patient data as there is little data available in pediatric patients.

c. For the purposes of this protocol, we will define age based parameters for eGFR as follows: Normal renal function not requiring dose adjustments if: >12 months: At least a GFR of >60 ml/min/1.73 m2. <12 months: A GFR of >40 ml/min/1.73 m2. Patients will be excluded from enrollment if baseline eGFR was <30 ml/min/1.73 m2

The creatinine should be measured using the IDMS (Isotopic Dilution Mass Spectrometry) technique to monitor the eGFR if available. Other methods are allowed but are not preferred. Laboratory testing using other methods will not be used to monitor the eGFR.

The population PK analysis was updated including data from 71 juvenile and adolescent patients with Chronic Atypical Neutrophilic Dermatosis with Lipodystrophy and Elevated Temperature (CANDLE), CANDLE related disorders, STING-associated vasculopathy with onset in infancy (SAVI), and Aicardi-Goutières syndrome (AGS). The analysis has shown that while kidney function, as expressed by estimated GFR, is a statistically significant patient cofactor of the PK characteristics of baricitinib in this multi-disease patient population, the effects of eGFR on the kinetics of this patient population were not clinically relevant as they relate to dosing and did not support dose adjustment for patients with eGFR less than 120 mL/min/1.73 m².

Appendix 4. Dose Escalation Schedule for Patients with eGFR 30- <60 mL/min/1.73 m2 or for Age <24 Months with abnormal eGFR (see footnote below^c)

If a change in the patient's weight during the study would place the patient in a different weight range changes over time are permitted.

		Morning Dose	Noon Dose	Afternoon Dose	Evening Dose	Total Daily Dose	Dosing Frequency
eGFR 30 - < 60 mL/min/ *	1.73 m ^{2b}						I
10-< 20 kg	Initial	1 mg	1 mg	0 mg	1 mg	3 mg	TID
	Escalation 1	1 mg	1 mg	1 mg	1 mg	4 mg	QID
20-< 40 kg	Initial	2 mg	-	_	1 mg	3 mg	BID
	Escalation 1	2 mg	_	_	2 mg	4 mg	BID
≥ 40 kg	Initial	2 mg	_	_	2 mg	4 mg	BID
	Escalation 1	3 mg	-	_	3 mg	6 mg	BID

BID = twice daily, eGFR = estimated glomerular filtration rate, QID = 4 times daily, TID = 3 times daily.

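### For newly screened patients over 2 years, the renal enrolment cut-off is eGFR <40 in Section 3.3.3 but <30, with no age split, in footnote c of Appendices 3 and 4

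*Combined protocol and SAP*

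**What the plan says.** Section 3.3.3 gives the renal exclusion in two consecutive bullets. The first excludes on an eGFR "based on the most recent available serum creatinine of <40 mL/min/1.73 m² if greater than 2 year of age". The second says that children with an eGFR below 40 "will not be enrolled, unless <24 months of age in which case a cut off of <30 ml/min/1.73 m2 will be used". Together they set a cut-off of 40, lowered to 30 only for children under 24 months.

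Footnote c of Appendix 3 first defines renal function that needs no dose adjustment, separately above and below 12 months of age. It then adds: "Patients will be excluded from enrollment if baseline eGFR was <30 ml/min/1.73 m2". Footnote c of Appendix 4 repeats the whole text. The exclusion sentence carries no age limit in either place.

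Appendix 4 is titled "Dose Escalation Schedule for Patients with eGFR 30- <60 mL/min/1.73 m2 or for Age <24 Months with abnormal eGFR", and Section 4.4.2 refers to it in the same terms: "See Appendix 4 for the dosing schedule for patients with eGFR 30 - <60 mL/min/1.73 m²". Section 3.1.2.1 has eligible patients start baricitinib on the regimens in Appendices 3 and 4.

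On enrolment, Section 4.4.1 says that entered patients are ineligible and "should be discontinued from the study if they meet any of the exclusion criteria listed in Section 3.4.2". On transfers from the compassionate use study, Section 3.3.1 says that they "will automatically roll into this study and do not need to meet the eligibility criteria outlined below".

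**The concern.** An enrolment threshold should have one value for each age group wherever it appears. Here the exclusion list and the dosing appendices differ for patients over 2 years, and the difference concerns baseline renal function for a drug that, according to Appendix 16, is cleared mainly by the kidneys.

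An error has a cost under the protocol's own terms. Section 4.4.1 requires strict adherence to the enrolment criteria and has a patient enrolled by mistake taken off the investigational product. Section 4.8 warns that abrupt discontinuation may provoke rebound inflammation, and Section 9.4.2.1.1 links discontinuation to neurologic decline. A misreading at screening would therefore not be harmless if found later.

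There is also a minor analysis consequence. Sections 3.3 and 6.4 analyse initially ineligible but approved subjects apart from those who meet every criterion, and that split needs one definition of eligible.

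**Working it through.** No sample size, power, error rate or event count is involved. The check sets the stated thresholds side by side for a newly screened patient (eGFR in mL/min/1.73 m²).

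| Age | Baseline eGFR | Section 3.3.3 | Footnote c, Appendices 3 and 4 |
|---|---|---|---|
| Over 2 years | below 30 | excluded | excluded |
| Over 2 years | 30 to below 40 | **excluded** | **cut-off not met** |
| Over 2 years | 40 or more | not excluded | cut-off not met |
| Under 24 months | below 30 | excluded | excluded |
| Under 24 months | 30 or more | not excluded | cut-off not met |

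Only the second row differs.

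**Could footnote c be an infant-only rule?** No. The sentence follows a definition that covers children both above and below 12 months, and it is not restricted itself.

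**Could it be about dosing rather than enrolment?** No. It speaks of baseline eGFR and of exclusion from enrolment.

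**Could it be an extraction fault?** Unlikely. The same complete sentence stands in two separate appendices.

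**Does the 30 to <60 dosing band add to the conflict?** Not by itself. Section 4.4.2 says that changes in "renal function may require dose changes as the individual falls within different categories in the tables in Appendices 3 and 4", so the lower part of the band can serve patients whose renal function falls on study. It can also serve children under 24 months and transferred patients. The inconsistency rests on footnote c alone.

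**Which text decides?** Section 3.3.3 excludes on any listed criterion and Section 4.4.1 makes enrolment depend on that list, which favours Section 3.3.3 as the operative text. But Section 4.4.1 cites the list as Section 3.4.2, as do Sections 3.3 and 4.3. In this version the list is numbered 3.3.3, and no sentence ranks it against footnote c.

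**What the band means at the bedside.** The protocol's Bedside Schwartz equation is eGFR = 0.413 × height / serum creatinine, with height in cm and creatinine in mg/dL. Rearranged, creatinine = 0.413 × height / eGFR. The band therefore runs from just above 0.413 × height / 40 up to 0.413 × height / 30. At an assumed height of 100 cm this is 41.3 / 40 = 1.03 to 41.3 / 30 = 1.38 mg/dL. Both limits scale in proportion to height.

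**How many patients?** The documents do not say. The only renal data are in Table 1, for 35 preliminary patients. Before study 29 were grade 0 and 6 grade 1 on eGFR; on study 19 were grade 0 and 16 grade 1. None was higher. The eGFR limits behind the grades are not given, so the table suggests a small number but cannot show that the band is empty.

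**The case against.** The strongest reply is that the texts do not strictly contradict each other. Footnote c gives a ground for exclusion; it does not say that anyone at 30 or above is eligible. A site can obey both by excluding a 3-year-old with an eGFR of 35 under Section 3.3.3, on whom footnote c is silent. The protocol also has only one exclusion list and ties enrolment to it, the 3.4.2 citation is plainly a leftover number, and footnote c sits under a dose table.

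Much of this stands, and it rules out two stronger readings. A reader might infer that the appendices would enrol and dose a patient over 2 years at 30 to below 40. They do not say so, because not meeting one exclusion cut-off is not permission to enrol. A reader might also infer that eligibility in this band is simply undetermined. That goes too far, since Sections 3.3.3 and 4.4.1 point to the exclusion list. General exclusions on the investigator's judgement of health status and screening laboratory values apply as well.

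What the reply does not remove is that a sentence expressly about baseline eGFR and enrolment gives a different number from the criteria for the same patients. It appears twice, beside the tables that staff consult to start treatment, and no text says that it yields to Section 3.3.3.

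**Conclusion.** The inconsistency is real and narrow. It is confined to newly screened patients over 2 years with a baseline eGFR from 30 to below 40. Transferred compassionate-use patients are outside it under Section 3.3.1, so it would be wrong to read it as touching every patient over 2 years in the band.

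It is more than clerical, because it concerns a decision threshold for a renally cleared drug. It is limited in weight, because the protocol's structure favours one text and the number affected is unknown and may be small. That last judgement assumes that new patients resemble the 35 in Table 1.

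A reader might infer that the efficacy analysis is put in doubt through the eligible group of Section 6.4. The documents do not support that. The plan already separates initially ineligible but approved subjects, the effect is at most on how a few patients are classified, and no endpoint, power or sample-size figure moves. The conclusion is only that the passages must be reconciled, not that either threshold is the right one.

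**What to change.** Reconcile Section 3.3.3 with footnote c of Appendix 3 and of Appendix 4, so that one enrolment threshold is stated for each age group and reads the same in all three places. One way is for the footnotes to refer to the exclusion criteria instead of restating a number. Correct the references to Section 3.4.2 in Sections 3.3, 4.3 and 4.4.1 so that they point to the exclusion list as it is now numbered. The choice of threshold belongs to the sponsor and the clinical team.

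The cost is a wording amendment. Under Section 9.8.7 it needs IRB approval and notice to the FDA. It calls for no new data, procedures or recalculation.
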